3. *Clinician-Administered PTSD Scale for DSM-5 (CAPS-5)* is a structured diagnostic interview and gold standard for assessing PTSD. It has excellent psychometric properties and diagnostic efficiency (Weathers, Keane, & Davidson, 2001). The scale also assesses social and occupational functioning, dissociation, and the validity of symptom reports. The CAPS was revised to accommodate the changes made in DSM-5, to reduce administration time, and to facilitate learning administration and scoring procedures. The CAPS for DSM-5 (CAPS-5; Weathers et al., 2013) now uses only a single 5-point ordinal rating scale to measure symptom severity. Symptom severity ratings combine information about symptom frequency and intensity obtained by the interviewer. CAPS-5 scores range from 0 to 80 with higher scores indicating greater PTSD symptom severity. At the same time, the CAPS-5 was revised with an eye toward maintaining backward compatibility with the DSM-IV version of the instrument. Because the measure is new, psychometrics and diagnostic cutoffs are still being evaluated. The CAPS-5 will be administered by certified independent evaluators (IE) blind to treatment status at the beginning and end of the intervention for all participants. Studies conducted near San Antonio and Fort Hood will be able to utilize IEs who receive training and ongoing support by the CAP Assessment Core. Remote studies will need to supply IEs for the various administrations of the CAPS-5. These staff will adhere to the Assessment Core's standardized procedures.
4. *PTSD Checklist for DSM-5 (PCL-5; Weathers, Litz, Keane, Palmieri, Marx, & Schnurr, 2013)* is similar in form to the PTSD Checklist (PCL) based on the DSM-IV (Weathers, Litz, Herman, Huska, & Keane, 1993). The PCL has excellent psychometric characteristics for screening and as a secondary indicator of PTSD symptom severity (see McDonald & Calhoun, 2010). The PCL-5 is a 20-item self-report measure, selected for its dimensional sensitivity, with higher scores reflecting greater PTSD severity. Scoring is based on how much the patient has been bothered by the symptoms in the past month on a scale from "0 = not at all" to "4 = extremely."

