11. **Quick Drinking Screen (QDS) self-report version (Sobell et al., 2003).** The QDS will be used to measure alcohol consumption. It consists of 4 items probing frequency and quantity of alcohol consumption. It will be administered in a self-report form. The QDS has been validated against the Timeline Followback daily estimation measure of alcohol use, and it shows good psychometric properties (Roy et al., 2008; Sobell et al., 2003). The QDS’s time-frame will be modified to match the “last two weeks” probed by the mandated depression and anxiety instruments for CAP studies (PHQ-9 and GAD-7). Like these other measures, the QDS can be administered frequently throughout CAP trials to track changes in alcohol use.
12. **Fagerstrom Test for Nicotine Dependence (FTND; Heatherton et al., 1991).** The Fagerstrom is a 6-item self-report measure that assesses severity of nicotine dependence. Questions probe both quantity of nicotine use (e.g., number of cigarettes per day) and pattern of use (e.g., time to first cigarette in morning). Respondents choose among response options, each of which is assigned a numerical value, with higher numbers corresponding to greater nicotine dependence. Scores on all items are summed to create a severity index with a range of 0 to 10, with higher scores indicating more severe dependence. The Fagerstrom scale has been shown to have high convergent validity with biochemical indices of nicotine use, and the measure has shown acceptable internal consistency (Heatherton et al., 1991). A review of 26 studies of the psychometric characteristics of the Fagerstrom found that it is a reliable instrument for measuring nicotine dependence in diverse settings and populations (Meneses-Gaya et al., 2009).
13. **Fagerstrom Test for Nicotine Dependence – Smokeless Tobacco (FTND-ST).** This is a modified version of the Fagerstrom Test that focuses on smokeless tobacco use, whereas the original Fagerstrom focuses exclusively on smoking. Like the FTND, the FTND-ST is a 6-item self-report measure of severity of nicotine dependence that has demonstrated convergent validity with biochemical indices of nicotine use (Ebbert et al., 2006; Ferketich et al., 2007). As on the original FTND, respondents choose among response options, each of which is assigned a numerical value, with higher numbers corresponding to greater nicotine dependence. Scores on all items are summed to create a severity index (range = 0–10).

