3. Clinician-Administered PTSD Scale for DSM-5 (CAPS-5)		X						X
4. PTSD Checklist for DSM-5 (PCL-5)		X		X	X	X		X
5. Life Events Checklist - 5 (LEC-5)		X						X
6. Deployment Risk and Resiliency Inventory-2 (DRRI-2) Combat and Postbattle Experiences Subscales		X						
7. Patient Health Questionnaire-9 (PHQ-9)		X		X	X	X		X
8. 'Structured Interview Guide for the Montgomery-Åsberg Depression Rating Scale (SIGMA).pdf'		X				X		X
9. Generalized Anxiety Disorder Screen (GAD-7)		X		X	X	X		X
10. Alcohol Use Disorders Identification Test (AUDIT) self-report version		X						X
11. Quick Drinking Screen (QDS) self-report version		X						X
12. Fagerstrom Test for Nicotine Dependence		X				X		X

13. Fagerstrom Test for Nicotine Dependence – Smokeless Tobacco		X				X		X
14. Insomnia Severity Index (ISI)		X				X		X
15. Snoring, Tired, Observed, Blood Pressure (STOP) Sleep Apnea Screen		X						
16. Patient Reported Outcomes Measurement Information System (PROMIS) Sleep Disturbance and Sleep-Related Impairment short forms		X				X		X
17. Depressive Symptoms Index – Suicidality Subscale		X				X		X
18. Self-Injurious Thoughts and Behaviors Interview short form		X				X		X
19. Veterans RAND 12-Item Short Form Health Survey (VR-12)		X						X
20. Brief Inventory of Psychosocial Functioning (B-IPF)		X						X
21. Health Questionnaire		X				X		X
22. Clinical Global Impressions (CGI)		X				X		X
Adverse Events Monitoring			X	X-X	X-X	X-X		X
Concomitant Medications/Treatment	X-X	X-X		X-X	X-X	X-X		X
Structural MRI			X					
Intrinsic Connectivity by Blood-Oxygen-Level-Dependent Functional MRI			X				X	
Motor threshold assessment			X				X	
irTMS Treatment (20 consecutive days)				X-X	X-X	X-X		
Participant Blind Form							X	
Independent Evaluator Blind Form								X

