Clinical Outcomes Data Analysis plan. All pre-treatment and post-treatment MRIs will be acquired and analyzed at the RII, however, all of the statistical analysis of the symptom scores for this project will be done upon completion of recruitment and termination group blinding. The primary efficacy outcome measure will be the PTSD Checklist (PCL-5) for symptoms assessed pre-treatment, weekly during treatment, post-treatment, and 1-month following the completion of treatment and the Clinician-Administered PTSD Scale for DSM-5 (CAPS-5) for the diagnosis of PTSD assessed pre-treatment and 1-month following the completion of treatment. The primary analysis will use mixed effects regression models. Secondary analysis will focus on changes in PTSD symptoms clusters, effects of the intervention in mood symptoms, functioning and cognitive outcomes. Types and rates of adverse events will be summarized and compared across the study groups. The durability of benefit and the clinical significance of PCL changes will be explored. Non-compliance to protocol as defined as missing two consecutive iTMS sessions or receiving less than 16 iTMS sessions during hospitalization at LRTC will be assessed for and evaluated in data analysis.

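### The only recall period given for the PCL-5 is the past month, yet this primary measure is taken at Days 7, 14 and 20 of a 20-day treatment; if that window is used, every on-treatment score includes pre-treatment days

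*Combined protocol and SAP*

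**What the plan says.** Item 6, Phase I: Baseline Assessment, measure 4 (PCL-5) gives the recall period: "Scoring is based on how much the patient has been bothered by the symptoms in the past month". No other section gives a different period or a separate form for repeat visits.

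The Clinical Outcomes Data Analysis plan makes the PCL-5 a primary measure, with "symptoms assessed pre-treatment, weekly during treatment, post-treatment, and 1-month following the completion of treatment". The other primary measure, the CAPS-5, is "for the diagnosis of PTSD assessed pre-treatment and 1-month following the completion of treatment". On method the plan says "The primary analysis will use mixed effects regression models"; it names no primary time point or contrast.

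The Table of Study Procedures puts the PCL-5 at baseline, at the Week 1, 2 and 3 visits (Days 7, 14 and 20) and at follow-up. It shows none in the post-treatment column (Days 21-24). Its treatment row is labelled "irTMS Treatment (20 consecutive days". The same table has the CAPS-5 only at baseline and follow-up, whereas measure 3 in the baseline list says that evaluators give it at the beginning and the end of the intervention.

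**The concern.** A past-month window is longer than the 20-day treatment. A patient who follows it literally on Day 7, 14 or 20 must include days before any stimulation, when the two arms cannot differ because of treatment. The active-sham difference at each on-treatment visit would be pulled toward zero, most at Week 1. The weekly trajectory in the mixed model would also be distorted.

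At stake is a missed or understated effect during and at the end of treatment. Under the schedule table, the Day 20 PCL-5 is the only PTSD symptom scale at the end of treatment. Because no primary time point is named, it cannot be assumed that the 1-month visit carries the primary test.

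**Working it through.** The plan gives no figure to reproduce: it states no power, effect size or SD, and it does not discuss recall overlap.

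**Inputs.**
- Recall window: past month, taken as 30 days (measure 4).
- Visits: Days 7, 14 and 20 (Table of Study Procedures).
- Treatment start: Day 1 if Day 20 is the 20th treatment day. Otherwise Day 3 to Day 5, since the scan is on Day 2-3 and treatment is expected one to two working days later (irTMS Treatment Sessions).
- Recall weighting and onset of effect: not in the documents, so assumed and ranged.

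**Step 1. Share of the window before treatment** = 1 - (treatment days so far)/30.

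| Start | Day 7 | Day 14 | Day 20 |
|---|---|---|---|
| Day 1 | 23/30 = 77% | 16/30 = 53% | 10/30 = 33% |
| Day 3 | 25/30 = 83% | 18/30 = 60% | 12/30 = 40% |
| Day 5 | 27/30 = 90% | 20/30 = 67% | 14/30 = 47% |

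**Step 2. Share of the Day 20 effect that the Day 20 score records** = weighted mean effect over the window, divided by the effect on Day 20. The weights are either equal or 0.5^(k/7) for k = 0 to 29 days back (a 7-day half-life). The effect is either constant from the first treatment day or proportional to the treatment day reached.

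- Constant, equal weights: 20/30 = 67% (Day 3 start 18/30 = 60%; Day 5 start 16/30 = 53%).
- Constant, half-life: (1 - 0.5^(20/7))/(1 - 0.5^(30/7)) = 0.862/0.949 = 91% (Day 3 start 88%; Day 5 start 84%).
- Linear build, equal weights: (1 + ... + 20)/30 = 210/30 = 7, and 7/20 = 35% (Day 3 start 171/30/18 = 32%; Day 5 start 136/30/16 = 28%).
- Linear build, half-life: 62% (Day 3 start 59%; Day 5 start 55%).

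**Step 3. The same for a past-week window at Day 20.**
- Constant effect: 100%.
- Linear build, equal weights: the mean of treatment days 14 to 20 is 17, and 17/20 = 85% (Day 3 start 15/18 = 83%; Day 5 start 13/16 = 81%).

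So part of the loss under linear build comes from averaging over earlier treatment days, and would remain with a one-week window.

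**Step 4. Follow-up.** One month after the last session, a 30-day window lies after treatment. The 1- and 3-month PCL-5 and the 1-month CAPS-5 therefore do not carry the problem.

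**The case against.** The strongest reply is that this rests on silence. The recall sentence is a general description in the baseline list, and the weekly form is not in the documents. A past-week form may be in use. That stands, and it makes the point conditional: a reader might infer that the trial's scores are diluted, but the documents do not show which wording patients saw.

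A reader might also take the QDS as proof that the authors change recall periods for repeated use and chose not to for the PCL-5. Its "time-frame will be modified to match the" two-week period of the PHQ-9 and GAD-7, and "the QDS can be administered frequently throughout CAP trials to track changes in alcohol use". But the stated purpose was to match those two scales, and in this trial's table the QDS is given only at baseline and follow-up. It is weak support. The AUDIT text (measure 10) is better evidence: because that scale covers 12 months, it limits administration to baseline in trials without long follow-up. This is general programme wording, and the table still marks the AUDIT at follow-up. It does show that the authors address recall when they think it matters.

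A third objection is that the end of treatment may not depend on the PCL-5. Measure 3 promises a CAPS-5 at the end of the intervention, and the CGI, whose severity part rates the patient at the time of assessment, is scheduled at Week 3. The CAPS-5 statement conflicts with the table and the analysis plan, so it settles nothing until reconciled. The CGI is a global rating, not a PTSD symptom scale.

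Finally, a reader might turn the recorded share into a required increase in sample size. The documents do not support that. They state no power, and the SD would also change with the window: a score averaged over 30 days would normally vary less than one averaged over 7, which would offset part of the loss.

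**Conclusion.** The point holds in conditional form. As written, the protocol applies a past-month scale at three visits inside a 20-day treatment. If that window is used, a third to three quarters of it precedes treatment with a Day 1 start (33% to 77%), and about half to nine tenths with a Day 5 start (47% to 90%). On-treatment differences are biased toward zero. Both arms share the window, so no false difference arises.

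The effect on the Day 20 comparison is uncertain. The recorded share runs from 91% (constant effect, 7-day half-life, Day 1 start) to 28% (linear build, equal weights, Day 5 start), and nothing in the documents narrows that range. The loss is therefore modest at one end and severe at the other. The 1- and 3-month PCL-5 comparisons and the 1-month CAPS-5 are essentially unaffected, so this is not a defect of the whole primary analysis. It should be corrected because the affected measure is primary and the change is cheap. Confidence is medium, because the weekly form is unseen.

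**What to change.** 1. In measure 4, state the PCL-5 recall wording for each visit. Use past-week wording at all efficacy visits (baseline, Days 7, 14 and 20, and follow-up), so that the mixed model works with one window.
2. Keep one past-month form at screening for the eligibility score of 25 (Item 5, inclusion criterion 3).
3. Reconcile the PCL-5 criterion under Discontinuation of Subjects with whichever form is used. A different window may change when the criterion is met; the rule itself is for the investigators.
4. Reconcile the CAPS-5 timing in measure 3 with the Table of Study Procedures and the analysis plan.

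**Cost.** Form wording and one extra 20-item form at baseline, with no added visit. Scores become less comparable with past-month studies, and follow-up scores cover only the last week. If treatment starts on Day 3-5, the Day 7 window still holds 2 to 4 pre-treatment days (2/7 = 29% to 4/7 = 57%).

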

Item 4 Purpose and rationale Insert purpose, objectives and research questions/hypotheses here. If you cut and paste from another document, make sure the excerpted material answers the question
	
We propose a randomized, double-blind, sham-controlled, 20 consecutive day trial of adjunct TMS to the right DLPFC in active duty service members and veterans with PTSD receiving an integrated and evidence-based treatment (i.e. TAU) for PTSD incorporating both adequate pharmacological approaches and Cognitive behavioral therapy (CBT) at Laurel Ridge Treatment Center (LRTC). In addition to TAU, consented patients will be randomized to receive irTMS in one of two treatment arms: Arm 1 delivers active irTMS to the right DLPFC. Arm 2 delivers sham TMS (inactive coil) to the right DLPFC. To ensure equivalent placebo effects across arms, sham TMS delivers the exact sound produced during active irTMS, therefore patients are unable to discriminate between sham and active TMS. Moreover, clinicians providing TAU at LRTC and researchers conducting clinical outcomes assessments will be blinded to each participants' treatment arm. Resting-state fMRIs (rs-fMRIs) will be used both for treatment planning (baseline imaging), which guides the individualized positioning of the TMS coil, and to characterize TMS-induced network connectivity (imaging treatment week 3). Self-report scales will be done weekly at LRTC. A 1-month post-treatment clinical follow-up will be conducted in person or over the phone to evaluate maintenance of clinical outcomes. Considering that depressive symptomatology, often meeting diagnostic criteria Major Depressive Disorder (MDD), is commonly observed in patients with PTSD, patients with comorbid PTSD and MDD won't be excluded from the study and we will also assess depressive symptoms throughout treatment at the same time intervals—i.e., baseline, weekly, and 1 month post-treatment.
 
Aim 1. Test whether compared with TAU plus sham irTMS, TAU plus adjunct active irTMS is associated with greater clinical improvement that differs in specificity to PTSD or depressive symptomatology according to the targeting of right DLPFC .
 
 Hypothesis 1. TAU plus adjunct active irTMS to the right DLPFC will be superior to TAU plus sham irTMS in relieving PTSD symptoms. 
Aim 2. Test for irTMS-induced changes in network functionality (plasticity) using rs-fMRI.
 
 Hypothesis 2a. Intrinsic connectivity will be attenuated by active irTMS in networks connected to the respective treatment sites, as tested by correlation with the number of sessions received at the time of scanning and by pre-treatment-to-post-treatment contrast. Hypothesis 2b. Treatment-induced decreases in connectivity will correlate with symptom improvement within and across treatment arms.

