Phase I: Baseline MRI. Once the participant has completed the psychological assessments required to determine inclusion/exclusion criteria, eligible participants will be taken from the LRTC to the Research Imaging Institute (RII) at UTHSCSA. When the participant arrives, the participant will undergo an anatomical and functional magnetic resonance imaging (MRI) session. Earplugs will be provided at every MRI session. MRIs use strong magnets and radio waves to non-invasively acquire images of organs and tissues. Unlike X-rays, MRIs do not expose subjects to radiation, therefore it is considered safe to obtain many MRIs in a single scanning session or over multiple days; the initial MRI scans may take up to 2 hours. In the event that the participant cannot tolerate the MRI procedure, they will be withdrawn from the study. Participants will be imaged at the RII using a research-dedicated 3T Siemens TIM/Trio MRI scanner (Siemens, Erlangen, Germany) with an eight-channel phased array coil. Structural imaging will be obtained only once, upon enrollment. Structural images will be used for iTMS treatment planning (described below) and for spatial normalization to a standard anatomical template. MRI images will be obtained two times (i.e. pre-treatment and post-treatment) and used to detect symptom-specific network abnormalities and treatment-induced plasticity. We will also perform motor threshold assessments for each patient (at pre-treatment and post-treatment, immediately after each MRI) to determine the correct intensity and train durations needed to safely deliver iTMS in each patient's 3-Week Treatment Phase. The post-treatment motor threshold assessment are important to the future establishment of safety guidelines for iTMS treatment of PTSD.

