robust and widely used pulse sequence for intrinsic connectivity modeling. BOLD images will be used for computing treatment plans and for testing for intrinsic connectivity changes by symptom score and with treatment. BOLD data will be acquired as 360 whole-brain volumes acquired with a TR = 2500 ms, TE = 30 ms, tip angle = 90°, 128 x 128 voxels, 1.7 mm x 1.7 mm, and 36 slices (4.0 mm thickness). This sequence requires ~ 15 minutes. Resting-state BOLD (15-min acquisition) will be used to map per-subject the voxel-wise intrinsic connectivity of DLPFC with the anterior cingulate cortex (ACC) and Precuneus; this will guide aiming parameters.

Motor Threshold Assessment. After the baseline MRI session, each patient will undergo a brief motor threshold assessment by single pulse TMS to their primary motor cortex hand region which elicits a contraction of the targeted hand muscle. The motor threshold assessment begins by locating the hand region and applying single pulses of TMS—with at least 5 seconds between successive pulses—at increasing levels of TMS intensity. We continue to ramp up the TMS intensity with each TMS pulse until we observe a contraction of the targeted hand muscle in 5 out of 10 pulses at a given TMS intensity. This TMS intensity will then be recorded as that patient's resting motor threshold. Using the patient's BOLD fMRI of the primary motor cortex, we can calculate their coil-to-cortex depth and use this information to determine the correct irTMS treatment intensity for the DLPFC and also determine the correct train duration needed to safely deliver 20Hz irTMS in each patient using published safety guidelines on appropriate train durations at specific TMS frequencies and intensities.

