The right DLPFC treatment target locations will be based on connectivity strength with ACC and Precuneus using region-seeded resting-state BOLD fMRI. Coil orientation will be corrected for the underlying gyral anatomy, using a T1-MRI derived cortical surface model to align the E-field according to the cortical column cosine model. Stimulation intensity will be corrected for the distance of the stimulation site from the scalp/coil surfaces. Intensity ranges will be individually adjusted for each patient—to deliver depth-corrected E-fields between 80 volts/meter and 95 volts/meter.

Sham TMS: An image-guided treatment plan will be computed for sham TMS subjects in the same manner as for active irTMS to ensure therapist blinding.

irTMS Treatment Sessions. All participants will continue with their TAU at LRTC (or its treatment clinics) including regular medication management encounters with their attending psychiatrist and therapy sessions as of their treatment. An effort will be made to limit the disruptions in patients' TAU by working research assessments and irTMS around their expected TAU programming. irTMS treatment visits will take place at the LRTC starting as soon as possible after the treatment plan is completed, expected to be 1-2 working days following baseline scanning.

irTMS Position/Holding. For each subject, the coil pose will be pre-computed from structural and functional MRI and stored as an individualized treatment plan. Each subject's treatment plan will be registered to his/her head by creating a scalp model with a high-resolution digitizer, an integrated component of the irTMS system. In each arm,

the TMS coil will be positioned and held by the robot (under the treatment technician's supervision).

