Intrinsic Connectivity by BOLD fMRI. Data will be analyzed using FSL's FEAT program. Head movements are corrected by affine registration using a 2-pass procedure. BOLD data will be normalized to MNI space single-patient template using the "unified segmentation" approach, followed by a 5-mm full width at half maximum Gaussian smoothing. Spurious correlations with nuisance variables are removed using a recently validated framework. Data are band-pass filtered preserving frequencies between 0.01 and 0.08 Hz. The time course of each seed region's BOLD signal will be extracted as the first eigenvariate of activity in all gray-matter voxels located within the respective cluster. To quantify resting-state functional connectivity linear (Pearson) correlation coefficients between the time series of the seeds (targeted DLPFC nodes of each patient's DLPFC-limbic and DLPFC-motor networks) and any other gray matter voxel will be computed. Voxel-wise correlation coefficients will be transformed into Fisher's Z-scores (with non-sphericity correction). These images will be used for iTMS treatment planning. The resting-state fMRI scan will also be used to assess, network-specific functional connectivity differences between each patient's pre-treatment and post-treatment scans.

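### The baseline scan that picks each DLPFC target is also the pre-treatment scan for Hypothesis 2a, so zero change is the wrong null for the connections used in selection, and no sham comparison is named

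*Combined protocol and SAP*

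**What the plan says.** Target selection is described in Item 6 under irTMS Treatment Planning: "The right DLPFC treatment target locations will be based on connectivity strength with ACC and Precuneus using region-seeded resting-state BOLD fMRI". The subsection on intrinsic connectivity for computing treatment plans says that this is mapped voxel by voxel in each subject from a 15-minute resting run. It also states the double use: "BOLD images will be used for computing treatment plans and for testing for intrinsic connectivity changes by symptom score and with treatment".

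There is no separate localiser scan. Under Phase I: Baseline MRI, imaging takes place at two time points only, one before and one after treatment. No split of the baseline run is described.

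The Neuroimaging Data Analysis Plan (Intrinsic Connectivity by BOLD fMRI) defines the "seeds (targeted DLPFC nodes of each patient's DLPFC-limbic and DLPFC-motor networks" and correlates them with every other gray-matter voxel. It says that the resulting images feed treatment planning, and then adds: "The resting-state fMRI scan will also be used to assess, network-specific functional connectivity differences between each patient's pre-treatment and post-treatment scans".

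Item 4, Hypothesis 2a, predicts that "Intrinsic connectivity will be attenuated by active irTMS in networks connected to the respective treatment sites". Two tests of this are given: a correlation with session count, and a comparison of the scans before and after treatment. No section names an active-versus-sham comparison for this hypothesis. The Sham TMS paragraph does say that sham participants' plans are computed in the same way as active ones.

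**The concern.** A site chosen because its measured connectivity was high on one run will, on average, have been helped by noise in that run. The post-treatment scan has fresh noise, so the measured value drifts back towards the site's true level. A test of each patient's change against zero counts that drift as a treatment effect. If the strongest positive coupling is preferred, the drift is downward, which is the direction that Hypothesis 2a predicts.

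The session-count correlation in Hypothesis 2a is exposed in the same way if the baseline scan enters as the zero-session point.

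Aim 2 is one of two numbered aims, and the abstract presents connectivity change as a possible biomarker of response. A significant within-arm fall between the target and the ACC or Precuneus could not be told apart from the effect of the targeting rule.

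**Working it through.** **No plan figure to reproduce.** The documents give no alpha, power, effect size or reliability for Hypothesis 2a.

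**Inputs from the documents.** 50 completers per arm (Item 6, Step-by-Step Methods); one pre and one post scan; targets selected on the pre scan in both arms.

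**Assumptions.** The site with the largest positive baseline value is chosen from K effectively independent candidates. Scan-rescan reliability is r. Single-scan variance is scaled to 1, so true variance is r and noise variance is 1 − r. TMS has no effect. The test is a paired t-test at two-sided 0.05, counting only significant falls (nominal 2.5%).

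**Formulas.** Let m and v be the mean and variance of the largest of K standard normal values.

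- Expected spurious fall = (1 − r) × m
- Variance of change at the selected site = (1 − r) + r(1 − r) + (1 − r)² × v
- Noncentrality of the paired t = √50 × fall / SD of change

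**Two corners of the range.**

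- K = 2 (m = 0.564, v = 0.682), r = 0.9. Fall = 0.1 × 0.564 = 0.056. Variance = 0.1 + 0.09 + 0.01 × 0.682 = 0.197, SD 0.444. Noncentrality = 7.07 × 0.056 / 0.444 = 0.90. Against the critical value 2.01, a significant fall has probability about 14% (13% in simulation).
- K = 10 (m = 1.539, v = 0.344), r = 0.5. Fall = 0.5 × 1.539 = 0.77. Variance = 0.5 + 0.25 + 0.25 × 0.344 = 0.836, SD 0.914. Noncentrality = 7.07 × 0.77 / 0.914 = 5.95, so the probability is over 99%.

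**Simulated rate of significant falls with no TMS effect** (800 trials per cell):

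| K | r = 0.5 | r = 0.7 | r = 0.9 |
|---|---|---|---|
| 2 | 53% | 35% | 13% |
| 3 | 88% | 63% | 27% |
| 5 | 99% | 91% | 47% |
| 10 | over 99% | 99% | 70% |

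With K = 1, meaning no selection, the rate is about 2.5%. The mean spurious fall runs from 0.06 to 0.77 single-scan SD.

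**Second parameterisation.** In Fisher z units, noise SD was 0.09 (from 2 × 0.07 Hz × 900 s = 126 effective degrees of freedom) or 0.15, and between-site true SD was 0.05 to 0.20. False falls occurred in 22 to 80% of trials at K = 2 and 90 to 100% at K = 10.

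**Where the bias reaches.** At K = 10, noise SD 0.09 and true SD 0.10, take a connection that was not itself used for selection. What matters is how strongly its noise correlates with the selection measure. At correlation 0 the test rejects in 5.4% of trials (two-sided, nominal 5%), at 0.3 in 36% and at 0.6 in 87%.

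**Sign.** In the same setting, choosing the most negative coupling gives a signed rise of 0.092 in Fisher z instead of a fall.

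**Alternatives under the null.** Comparing change between active and sham arms of 50 rejects in about 4 to 6% of trials, within simulation error of 5%. Selecting on one half of the baseline run and measuring on the other gives 5.5%. A site not chosen on its own connectivity gives 5.1%.

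**The case against.** The strongest reply is that this is a randomised, sham-controlled trial, that Hypothesis 2a attributes attenuation to active stimulation, and that sham targets are selected identically. An active-versus-sham comparison of change is therefore available and free of the bias. That is right, and it supplies the remedy. But the plan specifies the pre-to-post contrast and never states the between-arm one, so the protection lies in the design and not in the stated analysis.

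Second, much is unstated. Target selection is only said to be based on connectivity strength. The plan does not say whether the maximum is taken, which sign is preferred, how ACC and Precuneus are combined or how wide the search is. The abstract also mentions a meta-analytic input, which could limit selection on the patient's own noise. The sentence on pre/post differences names no seed and no test against zero, so carrying the targeted node over to it is an inference, though the natural one. These points limit what can be said about size and sign. They do not remove the double use of the scan.

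Three stronger readings are tempting and are not supported:

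- **A fall is guaranteed in every network tested.** Selection uses the ACC and Precuneus, while the analysis section names DLPFC-limbic and DLPFC-motor networks. Connections whose noise is unrelated to the selection measure, possibly the motor ones, carry no bias.
- **Hypothesis 2b's correlation with symptom improvement is weakened.** Under the same model, selection slightly reduces the variance of change (at r = 0.5: 1.00 with no selection, 0.92 at K = 2, 0.84 at K = 10). With an assumed patient-varying effect, the correlation did not fall (0.32, 0.33 and 0.34 respectively). A mean shift common to all patients does not weaken a correlation.
- **Aim 2 cannot be interpreted at all.** This would be true only if the sham arm were ignored.

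**Conclusion.** The concern holds for the within-patient contrast that the plan describes, on the ACC and Precuneus connections used for selection and on voxels whose noise correlates with them. There, zero change is not the right null. This rests on two readings: that change is measured from the targeted node, and that the site is chosen for strong coupling on the participant's own baseline run. The predicted direction, a fall, needs the further assumption that the coupling preferred is positive.

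The size cannot be fixed from the documents. The range of about 13% to over 99% is conditional on the assumed K and r, and would shrink towards 2.5% if selection were nearly absent or reliability nearly perfect. Even the mildest cell examined is about five times nominal (13 / 2.5 = 5.2).

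The issue is confined to the Hypothesis 2a imaging test in Aim 2. It should be corrected before the imaging data are analysed.

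**What to change.** In Item 4 (Hypothesis 2a) and in the Intrinsic Connectivity part of the Neuroimaging Data Analysis Plan:

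1. Make the test of Hypothesis 2a the active-versus-sham difference in pre-to-post change, measured from each participant's targeted node. This keeps the hypothesis about networks connected to the treatment site.
2. State that within-arm change at the selected target is descriptive and is not tested against zero.
3. Record the target-selection rule as used (sign, how ACC and Precuneus are combined, search region), and name the seed and networks for the change analysis.
4. Optionally, add a sensitivity analysis that selects on one half of the 15-minute run and measures on the other, or that uses a right DLPFC seed not taken from the participant's own baseline run. A common fixed seed should not be the main analysis, because it is not each patient's stimulated site.

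Targeting and treatment stay as they are, and no extra scans or patients are needed. The cost is precision: with equal arms, the standard error of a difference in change is √2 times that of one arm's change. With 50 per arm, the standardised difference detectable with 80% power at two-sided 0.05 is about 0.56.
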